10.3.4 Hypotheses Tested

For the primary endpoint of the proportion of patients who are responders according to the OMERACT-OARSI criteria, the following hypothesis will be tested.

$H_0: \pi \leq \pi_0$ versus $H_A: \pi > \pi_0$

Where π_0 is the hypothesized value for the proportion of responders. The value will be 30% in this study. This test will be tested using an exact binomial test. That is, given the sample size of n , the number of responders X , and the value of $\pi_0 = 0.30$, then probability that X or more events would be observed will be calculated as the p-value. Since this is a one sided test, the alpha level will be 0.025.

The primary hypothesis and these secondary hypotheses will be tested in a hierarchical manner with the primary first and the secondary hypotheses in the order listed. Using this approach, there is no adjustment necessary in the overall significance level. All testing will be conducted using an overall significance level of 5%. If the tests are one sided, the significance level will be 2.5%.

The secondary endpoints are represented by the proportion of patients who are responders as identified by the following response criteria:

- Improvement in pain and function (WOMAC A and WOMAC C) over baseline of $\geq 20\%$ and a 0.5 point absolute change
- Improvement in patient global assessment (PGA) over baseline of $\geq 20\%$ and a 0.5 point absolute change in PGA
- Improvement in pain and function (WOMAC A and WOMAC C) over baseline of $\geq 20\%$ and a 0.5 point absolute change compared to saline

The hypotheses for the first two secondary endpoints are identical and are:

$H_0: \pi \leq 30\%$ versus $H_A: \pi > 30\%$

These will be tested using the exact binomial test.

The hypothesis for the third secondary endpoint will be tested as:

$H_0: \pi_A \leq \pi_{HS}$ versus $H_A: \pi_A > \pi_{HS}$

Where π_A is the response rate from Ampion in this study and π_{HS} is the response rate of the saline control from previous single-injection Ampion studies. This will be tested using Fisher's exact test.

10.3.5 Exploratory Endpoints

None

10.3.6 Definition of Study Visits

This clinical trial has a total of 7 study visits, including telephone contacts, during the 12-week study (see Table 6.2). The time on study for each subject observation will be defined relative to Day 0/Baseline, the day of the initial dose. For analysis, the Baseline measure is the latest measure prior to initiation of treatment.

10.3.7 Number of subjects to receive study drug

A total of approximately 171 subjects (146 Ampion; 25 Saline) will be enrolled in the study to a single (1) intra-articular injection of 4 mL Ampion or 4 mL saline (6:1).

Since the sample size for adequate power of the primary and second secondary hypotheses is almost identical given the anticipated results of previous studies, the sample size for this study is based on the following hypothesis.

$$H_0:\pi \leq 30\% \text{ versus } H_A:\pi > 30\%$$

A sample size of 146 patients yields a greater than 90% power of rejecting the null hypothesis when the anticipated proportion under the alternative hypothesis is 45%.

10.3.8 Disposition of subjects

Disposition of subjects, including study completion status and response to therapy as measured by WOMAC A, WOMAC C and PGA subscores, will be summarized by age group, race, and gender for each of the analysis populations.

10.3.9 Interim analysis

There will be no interim analysis.

10.3.10 Blinding and randomization

All subjects will be randomized 6:1 to receive Ampion 4 mL or saline 4 mL as an intra-articular injection in the study knee.

A comprehensive presentation of the data management and statistical analysis plan will be approved by Ampio Pharmaceuticals, Inc. prior to final analysis to adjust for any changes to the protocol or unexpected issues in the study conduct and data that affect the planned analysis.

10.3.11 Data presentation**10.3.11.1 Demographic and Baseline Characteristics:**

Demographic (e.g., age, sex, race, and ethnicity) and Baseline characteristics (e.g., weight, height, prior injection of another intra-articular therapeutic for OA of the knee) summarized using descriptive statistics, overall and by treatment group for the ITT analysis population.

10.3.11.2 Medical History and Physical Examination:

The number and percent of subjects with past and current medical disorders at the time of randomization will be presented overall for the ITT analysis population. Results of any abnormalities documented from the abbreviated physical examination at Baseline and Week 12, will be summarized overall for the safety and ITT analysis populations.

10.3.11.3 Concomitant Medications or Treatments:

The number and percent of subjects receiving concomitant medications or treatments prior to and during the study and at the final visit will be tabulated and presented overall for the ITT

analysis population. Concomitant medications/treatments will be summarized using descriptive statistics and will be presented by type of drug (WHO DRUG classification) overall for the safety and ITT analysis populations.

10.3.11.4 Safety data:

Safety data will be evaluated by changes in vital sign measurements, physical exam, laboratory analysis, and the frequency and severity of AEs. Concomitant medication will be recorded for safety.

Adverse events:

The Investigator is responsible for monitoring the safety of subjects who have enrolled in the study. All AEs considered related, or possibly related to Ampion™, will be followed until the event resolves or stabilized without further change. Subjects will be followed for the occurrence of AEs until 12 weeks after the first dose of study medication.

Investigators are required to document all AEs occurring during the clinical trial, commencing with the first day of treatment through the end of study. AEs should be properly documented on the appropriate CRF pages.

The severity of AEs (mild, moderate, severe), relatedness (related, possibly related, unrelated) along with the duration, action taken, and outcome (e.g., study withdrawal) will also be recorded. In addition, events meeting the criteria of a Serious Adverse Event (SAE) must be reported to the Sponsor within 24 hours on the SAE reporting forms.

10.4 MISSING DATA

All data collected under this study protocol will be included in the assessment of subject safety. Missing or incomplete AE data will assume greatest relationship to study drug and/or severity.

For the primary effectiveness endpoint (WOMAC A, WOMAC C, and PGA), missing Week 12 values will be imputed when the ITT analysis population is used. Worst Observation Carried Forward (WOCF) will be selected as the primary method of imputing missing 12 Week data. Alternate imputation methods employed will include multiple imputations (SAS PROC MI and SAS PROC MIANALYZE) and Last Observation Carried Forward (LOCF). These sensitivity analyses will be conducted for the primary effectiveness endpoint, to ensure that the primary method of imputation chosen is robust with respect to imputation method used.

11 REGULATORY, ETHICAL AND LEGAL OBLIGATIONS

11.1 DECLARATION OF HELSINKI

The Principal Investigator will ensure that this Study is conducted in accordance with the most recent revision of the Declaration of Helsinki.

11.2 GOOD CLINICAL PRACTICE

The Study will be conducted according to the study protocol and to Standard Operating Procedures (SOPs) that meet the guidelines provided by the International Conference on Harmonisation (ICH) for Good Clinical Practice in clinical studies.

11.3 INSTITUTIONAL REVIEW BOARDS/ETHICS COMMITTEES

Before implementing this study, the protocol, the proposed subject informed consent forms and other information for the subjects, must be reviewed by a properly constituted committee or committees responsible for approving clinical studies. The IRB/IEC written, signed approval letter/form must contain approval of the designated investigator, the protocol (identifying protocol title, date and version number), and of the subject informed consent form (date, version).

Any change or addition to the protocol can only be made in a written protocol amendment, which must be approved by the Sponsor, the IRB/IEC and the Health Authorities.

11.4 REGULATORY AUTHORITY APPROVAL

Before this study is implemented, the protocol must be approved by the relevant regulatory authority.

11.5 INFORMED CONSENT

The investigator must fully inform the subject of all pertinent aspects of the trial including the written information approved/favorably assessed by the IRB/IEC.

Prior to the start of the pre-study examination, the written informed consent form must be signed and personally dated by the subject and by the physician who conducted the informed consent discussion. One copy of the written information and signed consent form must be given to each subject and 1 copy must be retained in the investigator's study records.

11.6 SUBJECT CONFIDENTIALITY AND DISCLOSURE

Data on subjects collected on eCRFs during the trial will be documented in an anonymous fashion and the subject will only be identified by the subject number, and by his/her initials. If, as an exception, it is necessary for safety or regulatory reasons to identify the subject, all parties are bound to keep this information confidential.

The investigator will guarantee that all persons involved will respect the confidentiality of any information concerning the trial subjects. All parties involved in the study will maintain strict confidentiality to assure that neither the person nor the family privacy of a subject participating in the trial is violated. Likewise, the appropriate measures shall be taken to prevent access of non-authorized persons to the trial data.

11.7 COLLECTION, MONITORING AND AUDITING STUDY DOCUMENTATION, AND DATA STORAGE

11.7.1 Collection of Data and Monitoring Procedures

This study will use a 21 CFR Part 11 compliant electronic data capture system (eDC). An electronic case report form (eCRF) is used for data recording. All data requested on the eCRF must be entered and all missing data must be accounted for.

The data will be checked for completeness and correctness as it is entered by the real-time online checks applied by the eDC system. Off-line checks will also be run to perform any additional data review required. Discrepancy reports will be generated accordingly and transferred to the study center for resolution by the investigator or his/her designee.

Accurate and reliable data collection will be assured by verification and cross-check of the eCRF against the investigator's records by the study monitor (source document verification), and the maintenance of a study drug-dispensing log by the investigator.

Before study initiation, at a site initiation visit or at an investigator's meeting, a Sponsor representative will review the protocol and case report forms with the investigators and their staff. During the study a monitor will visit the site regularly to check the completeness of subject records, the accuracy of entries on the case report forms, the adherence to the protocol and to Good Clinical Practice and the progress of enrollment. The monitor will ensure during on-site visits that study medication is being stored, dispensed and accounted for according to specifications. Key trial personnel must be available to assist the monitors during these visits.

The investigator must give the monitor access to relevant hospital or clinical records, to confirm their consistency with the case report form entries. No information in these records about the identity of the subjects will leave the study center. Monitoring standards require full verification for the presence of informed consent, adherence to the inclusion/exclusion criteria, documentation of SAEs and the recording of primary efficacy and safety variables. Additional checks of the consistency of the source data with the eCRFs are performed according to the study-specific monitoring plan.

11.7.2 Auditing Procedure

In addition to the routine monitoring procedures the Sponsor or the regulatory authority can conduct an audit or an inspection (during the study or after its completion) to evaluate compliance with the protocol and the principles of Good Clinical Practice.

The investigator agrees that representatives of the Sponsor and Regulatory Authorities will have direct access, both during and after the course of this study, to audit and review all study-relevant medical records.

11.7.3 Retention of Documents

The investigator must maintain source documents for each subject in the study, consisting of all demographic and medical information, including laboratory data, etc., and keep a copy of the signed informed consent form. All information on case report forms must be traceable to these source documents in the subject's file. Data without a written or electronic record will be defined before trial start and will be recorded directly on the case report forms, which will be documented as being the source data.

11.8 DISCLOSURE OF INFORMATION

All information provided to the investigator by Ampio Pharmaceuticals, Inc. or their designee, will be kept strictly confidential. No disclosure shall be made except in accordance with a right of publication granted to the investigator.

No information about this study or its progress will be provided to anyone not involved in the study other than to Ampio Pharmaceuticals, Inc. or its authorized representatives, or in confidence to the IRB, or similar committee, except if required by law.

11.9 DISCONTINUATION OF THE STUDY

It is agreed that, for reasonable cause, either the investigator or Ampio Pharmaceuticals, Inc., may terminate the investigator's participation in this study after submission of a written notice. Ampio Pharmaceuticals, Inc., may terminate the study at any time upon immediate notice for any reason, including the Sponsor's belief that discontinuation of the study is necessary for the safety of subjects.

11.10 STUDY REPORT, PUBLICATION POLICY AND ARCHIVING OF STUDY DOCUMENTATION

11.10.1 Study Report and Publication Policy

An ICH-compliant integrated clinical and statistical report will be prepared upon completion of the study and data analysis. The results of the study will be published in a relevant peer-reviewed journal, with authorship status and ranking designated according to the acknowledged contributions of participating investigators, institutions and the Sponsor.

11.10.2 Study Documents

The investigator must maintain source documents for each subject in the study, consisting of all demographic and medical information, questionnaires, including laboratory data, radiology data (as applicable), etc., and keep a copy of the signed informed consent form. All information on the e-case report forms must be traceable to these source documents in the subject's file.

Data without a written or electronic record will be defined before trial start and will be recorded directly on the e-case report forms, which will be documented as being the source data.

11.10.3 Archiving of Documents

Essential documents, as listed below, must be retained by the investigator for as long as needed to comply with national and international regulations. The Sponsor will notify the investigator(s)/institution(s) when the study-related records are no longer required. The investigator agrees to adhere to the document retention procedures by signing the protocol. Essential documents include:

- IRB/IEC/REB approvals for the study protocol and all amendments
- All source documents and laboratory records
- CRF copies (electronic copies on a CDROM)
- Subjects' informed consent forms (with study number and title of trial)
- FDA form 1572
- Any other pertinent study documents.

1. INTRODUCTION

This statistical analysis plan (SAP) outlines the proposed statistical methods to be implemented during the review and analysis of the data to ensure confirmation with categories determined by the CRF or the anticipated ranges for continuous variables and analysis of data collected within the scope of Ampion Protocol AP-003-C, “A Phase 3 Randomized Study to Confirm the Efficacy of an Intra-Articular Injection of Ampion™ in Adults with Pain Due to Severe Osteoarthritis of the Knee,” protocol version 1.3 dated 09 November 2017.

It is not intended that each and every table, listing, or graph will be included in the clinical study report (CSR). It is also possible that additional analyses will be conducted after review of the data. Any analyses or summaries not specified in the SAP, but performed after review of the data, will be identified in the CSR as post hoc.

2. OBJECTIVES

2.1 Primary Objective

The primary trial objective is to evaluate the clinical efficacy of a single intra-articular injection (4 mL) of Ampion.

2.2 Secondary Objective

The secondary trial objectives is to evaluate the safety of a single intra-articular injection (4 mL) of Ampion.

2.3 Study Design

This is a randomized, double-blind study with a 7-day screening period for each patient followed by a 12-week participation period. A total of 171 subjects with osteoarthritis of the knee (OAK) will be randomized 6:1 across 2 study arms, 4 mL Ampion™ and 4 mL saline. Deferred treatment of pain in the most severe form of the disease is unacceptable to both patients and physicians, and a larger saline arm is not possible or necessary for true comparator purposes in severe OAK subjects. The saline arm is for control of unintended bias and is not intended for analysis; only the active Ampion arm will be analyzed for efficacy.

Severe OAK is a painful, incurable, and progressive disease with a highly predictable outcome. Methodological challenges exist in this debilitated patient population where an unmet medical need exists and there is no valid, licensed or approved control or therapy for severe OAK patients. Therefore, in addition to the 6:1 randomization that is in place to eliminate any unintended bias, the study plan will assess a historic control using all the severe OAK saline-treated patients from all previously completed, randomized, saline-controlled, single-injection Ampion studies. The historic control for this clinical trial has a similar demographic and concomitant treatment profile to the current study, which

allows an effective comparison. Analysis of Ampion and its comparison to this historic saline-control group will ensure a meaningful comparison and quantitative assessment of Ampion effect, in addition to the demonstration of an effect of at least some minimum size, which is considered essential for acceptance of efficacy, specifically in cases where the active control is not a licensed product (e.g. some vaccine trials, IGIV trials, etc.).

The clinical effects of treatment on OAK pain will be evaluated during clinic visits at 6 and 12 weeks, and telephone contacts at 2, and 10 weeks, using the Western Ontario and McMaster Universities Arthritis Index (WOMAC[®]) osteoarthritis Index 3.1 and the Patient's Global Assessment of disease severity (PGA).

The WOMAC[®] is a validated scoring system and sets the standard for the patient response. In order not to bias the collection of data, only questions from the validated WOMAC scale will be asked of subjects.

Clinical benefit will be established by significant improvement on the WOMAC Index 3.1 and the PGA as assessed at Weeks 2, 6, 10, and 12. Safety will be assessed by recording adverse events (through 24 hours post-dose and at all follow up contacts) and physical examination and vitals (Baseline, Weeks 6, and 12), and clinical laboratory tests (Screening and Week 12).

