4.2 Secondary Hypotheses

The primary hypothesis and these secondary hypotheses will be tested in a hierarchical manner with the primary first and the secondary hypotheses in the order listed. Using this approach, there is no adjustment necessary in the overall significance level. All testing will be conducted using an overall significance level of 5%. If the tests are one sided, the significance level will be 2.5%.

For the secondary endpoint of the proportion of patients who are “controlled responders” to the OMERACT-OARSI criteria as defined in section 3.2 above, the following hypothesis will be tested.

$$H_0:\pi \leq \pi_0 \text{ versus } H_A:\pi > \pi_0$$

Where π_0 is the hypothesized clinically significant value for the proportion of responders. The value will be 30% in this study. This test will be tested using an exact binomial test. That is, given the sample size of n , the number of responders X , and the value of $\pi_0 = 0.30$, then probability that X or more events would be observed will be calculated as the p -value. Since this is a one sided test, the alpha level will be 0.025.

This composite analysis of OMERACT-OARSI “controlled responder” will be supported by Patient Global Assessment. Patient Global Assessment will be tested against the same hypothesis:

$$H_0:\pi \leq \pi_0 \text{ versus } H_A:\pi > \pi_0$$

The 3rd secondary trial endpoint, evaluating the improvement in a composite endpoint of pain and function (WOMAC A and C), defined as OMERACT-OARSI “controlled” response, will demonstrate that the active arm from this study is superior to analysis of all

historic saline-control arms from previous single-injection Ampion studies, will be analyzed using the following hypothesis.

$$H_0: \pi_A \leq \pi_{HS} \text{ versus } H_A: \pi_A > \pi_{HS}$$

Where π_A is the response rate from Ampion in this study and π_{HS} is the response rate of the saline control from previous single-injection Ampion studies. This will be tested using Fisher's exact test.

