4.3 Exploratory Analysis

If it is deemed to be clinically relevant, the analyses will be conducted using the appropriate adjustment methodologies.

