4.9 Data presentation

4.9.1 Demographic and Baseline Characteristics:

Demographic (e.g., age, sex, race, and ethnicity) and Baseline characteristics (e.g., weight, height, prior injection of another intra-articular therapeutic for OA of the knee) will be summarized using descriptive statistics, overall and by treatment group for the ITT analysis population. Demographic data for the historic control will be provided and summarized.

4.9.2 Medical History and Physical Examination:

The number and percent of subjects with past and current medical disorders at the time of randomization will be presented overall for the ITT analysis population. Results of any abnormalities documented from the abbreviated physical examination at Baseline and Week 12, will be summarized overall for the safety and ITT analysis populations.

4.9.3 Concomitant Medications or Treatments:

The number and percent of subjects receiving concomitant medications or treatments prior to and during the study and at the final visit will be tabulated and presented overall for the ITT analysis population. Concomitant medications/treatments will be summarized using descriptive statistics and will be presented by type of drug (WHO DRUG classification) overall for the safety and ITT analysis populations. Concomitant medication and treatment data for the historic control will be provided and summarized.

4.9.4 Safety data:

Safety data will be evaluated by changes in vital sign measurements, physical exam, laboratory analysis, and the frequency and severity of AEs. Concomitant medication will be recorded for safety.

Adverse events:

The Investigator is responsible for monitoring the safety of subjects who have enrolled in the study. All AEs considered related, or possibly related to Ampion™, will be followed until the event resolves or stabilizes without further change. Subjects will be followed for the occurrence of AEs until 12 weeks after the first dose of study medication.

Investigators are required to document all AEs occurring during the clinical trial, commencing with the first day of treatment through the end of study. AEs should be properly documented on the appropriate CRF pages.

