4.10 MISSING DATA

All data collected under this study protocol will be included in the assessment of subject safety. Missing or incomplete AE data will assume greatest relationship to study drug and/or severity.

For the primary effectiveness endpoints (WOMAC A, WOMAC C, and PGA), missing Week 12 values will be imputed when the ITT analysis population is used. The Worst Observation Carried Forward (WOCF) will be selected as the primary method of imputing missing 12 Week data. Alternate imputation methods employed will include multiple imputations (SAS PROC MI and SAS PROC MIANALYZE) and Last Observation Carried Forward (LOCF). These sensitivity analyses will be conducted for the primary effectiveness endpoint, to ensure that the primary method of imputation chosen is robust with respect to imputation method

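### The only planned Ampion-versus-saline test is an unadjusted comparison with non-randomised historic patients, and no baseline adjustment is fixed in advance

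*SAP*

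**What the plan says.** The primary endpoint and the first two secondary endpoints are one-sample exact binomial tests of the Ampion arm against 30%. Protocol 10.1.1 summarises the concurrent saline arm without comparison or inference. SAP 2.3 says that only the Ampion arm is analysed for efficacy.

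The third secondary endpoint is therefore the only test against saline. The historic control is built "using all the severe OAK saline-treated patients from all previously completed, randomized, saline-controlled, single-injection Ampion studies". SAP 4.2 defines the comparator rate as one that "is the response rate of the saline control from previous single-injection Ampion studies", tests it by Fisher's exact test with no covariates, and says that the endpoint "will demonstrate that the active arm from this study is superior" to the historic arms. It has a place in the controlled sequence: the hypotheses "will be tested in a hierarchical manner with the primary first and the secondary hypotheses in the order listed".

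On comparability, SAP 2.3 states that "The historic control for this clinical trial has a similar demographic and concomitant treatment profile to the current study". The planned support is descriptive:

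- SAP 4.9: "Demographic data for the historic control will be provided and summarized". The same is planned for concomitant medication.
- SAP 7, Listing 16.7: demographics and baseline characteristics of the historic control.

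On adjustment, SAP 4.3 says: "If it is deemed to be clinically relevant, the analyses will be conducted using the appropriate adjustment methodologies". SAP 6 allows the planned analyses to change, for instance after imbalance in covariates, with an explanation in the study report.

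**The concern.** A Fisher test of patients from different trials is a valid test of drug effect only if the historic saline patients would have responded as saline patients in this trial would. Response is calculated from baseline WOMAC A and WOMAC C, yet the similarity claim covers demographics and concomitant treatment. Nothing fixed in advance would correct a difference in those baseline scores. An adjustment chosen after the data are seen would be open to challenge.

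The stake is the claim against saline. Protocol 1.2 says that saline proved to be an active treatment, so beating 30% does not show that Ampion beats saline. Only this test addresses that question.

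**Working it through.** **The plan's own figure.** With n = 146 and a null rate of 30%, the smallest X with P(X or more) ≤ 0.025 is 56, where P = 0.0189. At 45%, P(X ≥ 56) = 0.956, so the stated power above 90% is reproduced. The documents state no power for the historic comparison.

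**Cohort size (Protocol Table 1.5.2).** KL 4 saline patients: 43 + 67 + 113 = 223. With 194 Ampion patients this makes 417, which equals the KL 4 counts of the three Phase 3 studies in Table 1.5.1 (75 + 132 + 210). The AIK study was also single-injection but had one KL 4 patient, so it could change the 223 by at most 1.

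**Entry criteria side by side.**

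| | This trial (Protocol 4.3) | Earlier studies (Protocol 1.5 summary) |
|---|---|---|
| KL grade | 4 | 2–4, cut to KL 4 by SAP 2.3 |
| WOMAC A | at least 1.5 | at least 1.5 |
| WOMAC C | at least 1.5 | not mentioned |
| Contralateral WOMAC A | below 1.5 | not mentioned |

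Two restrictions are shared. The other two may or may not have applied, because the earlier protocols are not available.

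**False-positive rate under a shift.** Fisher p-value for x Ampion responders out of t in total: Σ over k ≥ x of C(146,k)·C(223,t−k)/C(369,t). The null hypothesis is rejected when p ≤ 0.025. The hierarchy also needs the same controlled response to beat 30%, so x ≥ 56. All outcomes were enumerated with no drug effect, the historic rate as assumed, and the current population shifted by the points shown. Rejection, %:

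| Assumed historic rate | −5 | −3 | 0 | +3 | +5 |
|---|---|---|---|---|---|
| 25% | 0.00 | 0.00 | 0.02 | 0.39 | 1.70 |
| 30% | 0.01 | 0.06 | 0.72 | 4.31 | 10.53 |
| 35% | 0.08 | 0.33 | 1.84 | 6.84 | 13.61 |
| 40% | 0.12 | 0.40 | 1.95 | 6.81 | 13.36 |
| 45% | 0.13 | 0.43 | 1.98 | 6.78 | 13.19 |
| 50% | 0.13 | 0.43 | 1.95 | 6.64 | 12.96 |

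The primary and PGA tests, which also come earlier in the sequence, are not modelled. The primary adds no real barrier, since every controlled responder meets its two-of-three rule. The PGA test can only lower these figures.

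**What adjustment can and cannot do.** Simulation with 20,000 runs per case, an assumed +5 point shift, one standardised baseline covariate with a log-odds slope of 0.5 per SD, and a baseline gap of 0.45 or 0.43 SD in the measured case. Rejection, %, at historic rates of 35% / 45%:

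| Cause of shift | Fisher | Adjusted alone | Both required |
|---|---|---|---|
| None | 1.7 / 2.1 | 2.1 / 2.6 | 1.5 / 1.7 |
| Measured baseline score | 13.8 / 13.0 | 2.5 / 2.5 | 2.5 / 2.5 |
| Unmeasured | 13.3 / 13.1 | 16.2 / 16.4 | 12.3 / 12.1 |

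The measured case is favourable by construction, because the whole shift comes from the covariate adjusted for.

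**Evidence on drift.** Heterogeneity of mean pain change in the three earlier saline arms, with weights n/SD² of 52.4, 78.1 and 156.0 and a weighted mean of −0.616: Q = 0.591 + 0.001 + 0.178 = 0.77 on 2 df. That shows no sign of heterogeneity.

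**The case against.** The strongest reply is that the cohorts are closely aligned and the plan leaves room to adjust. Much of this stands. Both groups are KL 4 with the same pain floor. Listing 16.7 covers historic baseline characteristics, so WOMAC and PGA are unnamed there but not excluded. SAP 6 foresees covariate imbalance. The earlier saline arms look alike in mean pain, and the Ampion KL 4 responder rates in Table 1.5.3 span only 57.7% to 59.7%. But neither comparison concerns controlled response on saline or the current entry rules, and permission to adjust is not pre-specification.

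A reader might infer more than the documents support:

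- *That the historic patients are known to differ, or that the test is known to favour Ampion.* Absence from a summary paragraph does not show that a criterion was absent. Symptom duration over 6 months is no evidence either: Protocol 1.5 gives it for the earlier studies, and footnote 1 of the SAP schedule quotes it as current.
- *That saline volumes differed.* AP-003-A tested two Ampion volumes and supplies 43 of the 223 (19%), but its saline volume is not given.
- *That missing-data handling favours Ampion.* SAP 4.10 says "missing Week 12 values will be imputed when the ITT analysis population is used", and WOCF is stated only for this trial. Applied to current patients alone, it would generally lower the Ampion rate, unless missing historic patients were scored more harshly.
- *That the adjusted test should replace Fisher.* Under an unmeasured cause it rejects more often (about 16% against 13%).

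**Conclusion.** The point holds as a gap in pre-specification and should be fixed. The only claim against saline rests on asserted comparability, with no fixed analysis of the baseline scores that define response. No actual imbalance or error inflation has been shown.

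The figures of about 7% and 13–14% rest on an assumed historic rate of 35–50%, assumed favourable shifts of 3 and 5 points, and 223 historic patients. They shrink at 30% and vanish at 25%. It would be wrong to read them as the trial's type I error: this is the last test in the hierarchy, and the three tests before it do not use the historic data. Confidence is high that adjustment is not pre-specified. The size and direction of any bias are unknown.

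**What to change.** Before unblinding:

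1. **SAP 2.3.** Name the studies and the saline volumes in the historic cohort. Score historic patients with the same controlled-responder rule and WOCF. Keep all KL 4 saline patients for Fisher, and use restriction to baseline WOMAC C of at least 1.5 as a sensitivity analysis. Apply no contralateral filter unless every study recorded that score, since it would otherwise select unevenly.
2. **SAP 4.2.** Keep Fisher as the hierarchy test. Pre-specify a patient-level logistic model giving a standardised risk difference, adjusted for baseline WOMAC A, WOMAC C, PGA, age, sex and weight. Include no study term, because study and treatment are fully confounded in this comparison. Claim superiority over historic saline only if Fisher is significant and the adjusted one-sided 97.5% lower bound exceeds 0. Do not use the adjusted test alone.
3. **Tables.** Show baseline WOMAC A, WOMAC C and PGA for historic and current patients. Place the concurrent saline controlled-response rate, with its confidence interval, beside the historic rate, descriptively only. It can reveal only gross drift: 11/25, for example, has an exact 95% interval of 24% to 65%.
4. **Interpretation.** State that adjustment removes bias from measured baseline differences only, and that unmeasured between-trial drift remains.

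The cost is SAP text, programming on data the sponsor should already hold, and a recorded change to the success criterion in Protocol 10.3.4. Requiring agreement lowers simulated power from 77.7% to 76.9% (45% v 60%, no shift, one covariate); the six-covariate cost has not been computed. Keeping all historic patients for Fisher avoids a larger loss: exact power falls from 77.8% to 73.7% or 70.8% if restriction left 178 or 156 of the 223 (assumed removal of 20% or 30%).
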